#### 4.5. Data management:

Participants will be assigned unique ID numbers, which will be entered into databases and used on study forms. Using existing protocols, we will secure all records and files in compliance with VA data security policies. Electronic transmissions will be HIPPA compliant, and PAP equipment data transmissions will adhere to data security and data transfer policies. Original study forms will be archived and stored in locked cabinets in approved areas. Datasets will be cleaned by screening for out-of-range values, and comparing a random sample of 10% of entered data to original data collection forms. Problems with data entry will be addressed in an ongoing manner. Double entry procedures will be used on a 10% random sample of cases in each dataset, with additional training and review of data if errors are identified. Cleaned data will be scored and aggregated, then data will be merged into one main database for statistical analyses.

### 4.6. Data analysis plan:

**4.6a. Study Design Considerations:** The study design and data analysis will follow the CONSORT criteria for randomized controlled trials (RCTs). Participants will be randomly assigned to the treatment or control group as described in **Section 4.4b**. Randomization should produce groups that differ only by chance at baseline; nevertheless, the adequacy of randomization will be assessed by comparing the groups on all outcomes as measured at baseline. We will follow intention-to-treat (ITT) principles. While we anticipate some participants will not complete the intervention; we will continue to collect follow-up data from all randomized patients whether or not they complete the intervention program to which they are assigned. We anticipate no more than 10% of participants will have missing or incomplete follow-up data. To improve retention and reduce the risk of missing data, participants will be offered monetary incentives for completing follow-up assessments, regardless of whether they complete the intervention. In our recent studies of Veterans with disabilities, we were able to obtain follow-up data for up to 6 months in 92% of randomized participants. We have achieved this high follow-up rate by developing strong relationships with study participants, keeping them engaged and invested in the project, and making necessary accommodations to gather outcome data. While we do not anticipate differential attrition, we will compute the completion rate for each group (BEST and control) and compare completion rates to determine test for differences as a function of group. We will also compare baseline characteristics among those who have complete versus incomplete follow-up data to test for systematic attrition. To preserve the equivalency formed by randomization, ITT analyses will include all randomized participants for hypothesis testing. Since ITT analysis requires complete data, missing data will be imputed using multiple imputation. Sensitivity analyses will be performed comparing the ITT (with imputation) results to results for those with complete data (anticipated N=56). We have allowed for a 10% missing data rate in sample size computations. We anticipate randomizing 62 individuals (31 per group) to achieve a final total sample with complete outcome data at the 3-month followup of N=56 (28 per group). We do not anticipate additional attrition after 3 months since follow-up data beyond that time point will be gathered with remote telemonitoring.

**Overview of sample size computations:** Power computations were performed using the Stata power command. To determine the required sample size for the study, we determined the hypotheses for which we require the largest sample size. In this study, Aim 2 requires the largest sample size (n=56 with complete data; N=62 total randomized). We conducted the power analysis for Aims 1 assuming the sample size of N=56 required to address Aim 2. Given the exploratory nature of Aim 3, these tests were not considered in determining the required sample size for the overall study.

4.6b. Data Analysis and Sample Size Calculation for Aim 1: This aim examines the efficacy of the BEST program on PAP adherence. The main outcome will be the proportion of nights (out of 30 nights) with >4 hours of PAP use, as measured by the PAP machine itself. PAP adherence will be computed for the first 30 days (month 1), and for each subsequent 30-day period (months 2-12). All participants will be measured for at least 180 days, thus providing at least 6 months of data for all participants. PAP adherence rates beyond month 6 will be computed for participants who enrolled early enough to provide such data. Because adherence data will be gathered remotely using existing telemonitoring technologies in which PAP machines transmit use data to a cloud-based server, complete data is expected for each person. In an ongoing VA-funded study of PAP adherence being conducted by [name] research group, PAP adherence data or confirmed non-use has been obtained in 100% of participants using this method. The proportion of nights a patient uses PAP for 4 or more house will be computed by summing nightly scores (1=PAP used at least 4 hours; 0=PAP used less than 4 hours) and dividing the sum by the number of observations (i.e., 30 nights). Denoting  $\hat{p}_{ij}$  as the proportion of nights for person "i" in month "j", the sampling distribution of  $\hat{p}_{ij}$  will have an expected value equal to  $p_i$  (the true proportion who use PAP in the population in month "i") and the standard deviation of this sampling distribution is equal to  $sqrt(N*p_i *(1-p_i))$ . Further, based on the central limit theorem the sampling distribution of these monthly proportions,  $\hat{p}_i$  is expected to be normally distributed, justifying the use of normal theory statistical methods for the analysis of monthly PAP adherence.

[figure not shown]
Mixed-effects models will be used to compare monthly PAP adherence rates for the BEST program versus control program. When applied to longitudinal designs, mixed-effects models accommodate incomplete data across time points (such as arises in this study where only some participants will have data beyond six months) and can permit specification of a wide variety of residual covariance structures. PAP adherence will be analyzed using a 2 by 12 factorial mixed-effects model with a fixed intercept, where treatment group is a two-level between subjects factor (i.e., BEST versus control) and time is a 12 level categorical repeated measures factor (i.e., month 1, month 2, ... month 12). This approach will allow us to examine potential non-linear trends in the data which would not be readily apparent if time were treated as a continuous variable. The Bayesian Information Criteria (BIC) will be used to identify and select the best fitting residual covariance structure. Using the mixed-effects model, the difference in adherence rates between the BEST program and control group will be assessed and tested at each month.

Hypothesis 1a will be assessed evaluating the significance of the difference in adherence rates between the BEST program and control groups in months 1-3 (during the BEST program intervention).

Hypothesis 1b will be assessed by testing the significance of the difference in adherence rates between the BEST program and control groups in months 4-6 (after the BEST program has ended).

**Figure 6** illustrates four possible patterns of results Pattern 1 suggests the BÉST program immediately improved PAP adherence and effects were sustained over time. Pattern 2 shows that the BEST program improved PAP adherence during the treatment period; however, effects later diminish. Pattern 3 shows that the

BEST program improved PAP adherence gradually during the "treatment" period and effects were sustained over time. Pattern 4 also shows that the BEST program improved PAP adherence gradually; however, effects later diminished, These patterns will be statistically dissected to distinguish between immediate vs. gradual gains in pap adherence during the "treatment" phase, and between "sustained" and "diminishing" effects during the posttreatment phase (refer to [name] 2012).

Hypothesis 1c will be assessed by testing the significance of the difference in the adherence rates between the BEST program and control groups in months 6-12. Further analyses will be performed by graphically representing the results (as illustrated **Figure 6**: Possible patterns of results illuminated by the proposed analysis. in **Figure 6**, with 12 instead of 6

months), and further analyses of treatment maintenance versus diminution of effects will be statistically considered.

**Power Analysis for Hypotheses 1a-c:** As described above, the power with respect to Aim 1 was computed assuming a sample size of N=56 with complete data (required to address Aim 2; total N=62). This aim focuses on the difference between the two groups in terms of the average proportion of nights of PAP use  $\geq$ 4 hours per month. The standard deviation (SD) of this proportion is most conservatively estimated as SD= 0.0913 [computed as sqrt(.5\*(1-.5)/30)=.0913]. Given this SD, alpha=0.05 and power=.80, the study can detect a difference in the average proportion of nights of PAP use  $\geq$ 4 hours of 7% between intervention and control for a given month. In interpreting the results, however, we will focus on larger more clinically-important effects. This study will have ample power to detect these. For example, using the same sample size and alpha, the power to detect a 10% difference between groups would be power=.98. The power to detect a 20% difference would exceed power=.999. We would consider a difference of less than 10% (even if statistically significant) not clinically meaningful. We would consider a difference of 10% or more to be a clinically relevant difference. We would consider a difference of 30% or more to be a substantial and very clinically meaningful difference.

**4.6c. Data analysis and Sample Size Calculation for Aim 2:** This aim compares outcome measures beyond PAP use that are expected to improve as a result of the BEST program, compared to the control program. The outcome variables tested will include patient-reported sleep quality (hypothesis 2a), overall functioning (hypothesis 2b), quality of life (hypothesis 2c), and respiratory function (hypothesis 2d).

**Data Analysis for Hypotheses 2a-d.** These hypotheses will be tested using ANCOVA models to compare groups (BEST vs. control) for each of main outcome measured at post-treatment, after adjusting for baseline measurement of the outcome as a covariate. Compared to a "split-plot ANOVA" or an analysis of change scores, this strategy offers greater statistical power and better controls for possible baseline differences.

**Power Analysis for Hypotheses 2a-d. Table 7** shows the required sample size as a function of the standardized effect size and the correlation between posttest and baseline scores to achieve 80% power using a two-tailed alpha of 0.05. Cohen describes an effect size of d=0.8 as large, d=0.5 as medium, and d=0.2 as small. **Table 7** focuses on the combination of effect sizes and pretest-posttest correlations that would achieve power of .80. To evaluate plausible pretest-posttest correlations for the measures associated with hypotheses 2a-c, we assessed baseline to 4-month follow-up measures in a RCT of a sleep intervention for Veterans with disabilities. These are presented in detail below for each of the three hypotheses. **Table 7** shows that under the most pessimistic scenario (assuming no correlation between pre-test and post-test measures), this study has sufficient power to detect a large effect (*d*=0.75). As the purpose of this study is to find clinically meaningful effects (i.e., effects that tend to be large), this power analysis suggests sufficient power to detect such effects for all outcome measures. However, our prior research found very substantial pretest/posttest correlations (e.g., r=.75) which would permit detection of smaller effects (i.e., medium effects of d=0.50). Using the lower confidence limits still found substantial correlations (e.g., r=0.56) suggesting that this study will have the ability to detect all effects of d=0.63 or larger with a sample size of n=56 with complete 3-month follow-up data. To achieve this, we will randomize 62 subjects into intervention vs. control.

**Table 7**. Required total sample size as afunction of effect size and pre-test/post-testcorrelation for 80% power, alpha=.05.

Sample	Effect Size	Pretest/Posttest
Size	(Cohen's d)	Correlation
	d=0.50 (medium)	r=0.75
N=56	d=0.55	r=0.68
N-50	d=0.60	r=0.60
	d=0.63	r=0.56

Hypothesis 2a: To estimate the pretest-posttest correlation, we used our prior research showing a baseline-4-month correlation for PSQI of r=0.74 (95% CI=[.56,.86], N=40). Choosing

d=0.65	r=0.50
d=0.70	r=0.36
d=0.75	r=0.00

the lower confidence limit (r=.56) implies sufficient power to detect an effect size of Cohen's d=.63 (an effect somewhat larger than a medium effect) with N=56 (**Table 7**). Choosing the observed correlation (r=.74) implies sufficient power to detect an effect size of Cohen's d=.50 (a medium effect). Assuming no correlation (r=0.00), the study could still detect an effect size of Cohen's d=.75 (a large effect).

Hypothesis 2b: In the same preliminary data we found the baseline-4-month correlation of instrumental measures of daily living (IADLs) was r=.81 (95% CI=[.67, .89[). Using the lower confidence limit suggests the ability to detect an effect of d=.55 (slightly larger than medium effect).

Hypothesis 2c: To inform the power for this hypothesis, we examined baseline-4-month correlations for PHQ9 and FSS in our prior work. The correlation for PHQ9 was r=.79 (95% CI=[.64,.89], N=40), and for FSS, r=.76 (95% CI=[.57,.87], N=36). Using a conservative approach (lowest lower confidence interval = 0.57), an effect size of 0.63 could be detected with a sample size of 56 (See **Table 7**). Assuming the lowest observed correlation (r=0.76), the study would have sufficient power to detect an effect of d=0.50 (a medium effect). Our **Preliminary Data** shown in section 3.6 indicate large treatment effects comparing a behavioral sleep program vs. attention-control in terms of FSS ( $\omega^2$ =64%) and PHQ9 ( $\omega^2$ =35%). We believe similarly "large" effects for these outcomes are likely in the proposed study.

Hypothesis 2d: The main respiratory function outcomes are PFTs (i.e., upright and supine respiratory function/forces) measured at 3-months. While we have no prior data on pretest/posttest correlations for these measures, our prior research has found a the SD for FVC when measured sitting is 17.1, and 15.7 when supine. Considering a 12% change as clinically relevant, this implies an improvement, expressed as Cohen's d=.70 (sitting, 12/17.1) and d=.76 (supine 12/15.7). **Table 7** shows that there would be sufficient power to detect a 12% improvement in sitting respiratory function (corresponding to d=.70) given a correlation of r=.36 in from baseline to 3 months. Likewise, there would be sufficient power to detect a 12% improvement in supine respiratory function (corresponding to d=.76) regardless of the size of the correlation.

4.6d: Analysis plan for Exploratory Aim 3: This aim considers whether the BEST program is more effective for subgroups of patients such as those with depression, insomnia or bladder dysfunction. For categorical measures, grouping variables will be coded as 0/1. For continuous measures (such as ISI score), participants will be categorized into groups, using clinical cutoffs. If such cutoffs yield highly imbalanced groupings, we will consider a median split. For a given variable, each grouping variable will be interacted with treatment group and introduced into each analysis described in Aims 1 and 2. The test of the interaction will assess whether the treatment is more effective for one subgroup than another.

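### Hypotheses 1b and 1c (months 4-6 and 6-12) have no rule for turning monthly tests into one decision, and the SAP does not mention them

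*Protocol*

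**What the plan says.** Protocol section 4.6b analyses monthly PAP adherence in a group-by-month mixed model with month as a 12-level factor. The only unit of testing it names is the month: "the difference in adherence rates between the BEST program and control group will be assessed and tested at each month". The hypotheses are framed over windows: 1a covers months 1-3, 1b concerns the "program and control groups in months 4-6 (after the BEST program has ended", and 1c covers months 6-12. Month 6 belongs to both 1b and 1c. The section does not say whether one significant month, every month, a joint test or an average decides a hypothesis, and it gives no adjustment for several months.

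The Aim 1 power paragraph is headed as covering all three hypotheses, but the detectable difference is one "of 7% between intervention and control for a given month".

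On maintenance of effect, 4.6b says the patterns in Figure 6 will be separated statistically. It names no contrast.

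The SAP (approved April 2, 2020; the protocol is dated April 4, 2019) has a single Hypothesis 1, one outcome (nights out of 90) and one two-sample t-test. It does not mention 1b or 1c.

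**The concern.** A window of 3 or 7 months tested month by month yields 3 or 7 p-values. Without a rule fixed in advance, the same data can support or fail to support a durability claim, depending on how the p-values are read once results are known. One favourable month could be taken as success, or one weak month as failure. Durability after the programme ends is what 1b and 1c exist to show, and the protocol commits to 180 days of data on every participant to show it. The stated power does not help, because it applies to a single month and to none of the windows.

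**Working it through.** **Inputs from the protocol.** Section 4.6a gives "N=56 (28 per group" with complete data. Section 4.6b states that the SD of a monthly proportion "is most conservatively estimated as SD= 0.0913", and sets the error rates: "Given this SD, alpha=0.05 and power=.80, the study can detect a difference" of 7 points. Two-sided testing is stated for Aim 2 ("using a two-tailed alpha of 0.05") and is assumed here for Aim 1. It reproduces the Aim 1 figures.

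**The plan's own figures.** SE of a one-month difference = 0.0913 × √(2/28) = 0.0244.
- 7 points: 0.07/0.0244 = 2.87; noncentral-t power 0.805 (stated 0.80).
- 10 points: 0.10/0.0244 = 4.10; power 0.981. The protocol says "the power to detect a 10% difference between groups would be power=.98".

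Both reproduce, for one month.

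**Assumption.** The documents give no correlation between the monthly arm differences. I use 0.7 to 0.9, both exchangeable and AR(1), with independence as a reference. The effect is constant within a window and gives 80% power in one month (noncentrality 1.96 + 0.84 = 2.80). Correlated cases are simulated from multivariate normal test statistics.

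**Decision rules for one hypothesis**

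| Rule | Quantity | 3 months | 7 months |
|---|---|---|---|
| Any month significant | Type I error, independent | 1 − 0.95³ = 14.3% | 1 − 0.95⁷ = 30.2% |
| Any month significant | Type I error, correlation 0.7-0.9 | 8-11% | 11-23% |
| Every month significant | Power, independent | 0.80³ = 51% | 0.80⁷ = 21% |
| Every month significant | Power, correlation 0.7-0.9 | 64-72% | 44-67% |
| One averaged contrast | Type I error | 5% | 5% |
| One averaged contrast | Power, correlation 0.7-0.9 | 83-90% | at least 83% |

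For the averaged contrast under exchangeable correlation ρ, the SE relative to one month is √((1 + (k − 1)ρ)/k), and power = Φ(2.80/that ratio − 1.96). With k = 3 and ρ = 0.9 the ratio is √(2.8/3) = 0.966, so power = Φ(0.94) = 83%. With k = 7 and ρ = 0.9 it is √(6.4/7) = 0.956, again 83%. The 90% at the upper end for 3 months comes from AR(1) at 0.7.

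The 7-month figures assume all 56 participants. The protocol expects only some to have data after month 6, so actual power for 1c is lower.

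**At 10 points.** On the protocol's SD, the every-month rule has 96-97% power for 3 months and 92-96% for 7.

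**Change between windows.** Suppose the averaged months 1-3 contrast has 80% power and the effect then halves. With the one-month SE as the unit:
- Exchangeable 0.9: window variance (1 + 2 × 0.9)/3 = 0.933; variance of the between-window difference 2 × (1 − 0.9)/3 = 0.067. The fall is 2.80 × √0.933/2 = 1.35, and 1.35/√0.067 = 5.2. Power is over 99%.
- Exchangeable 0.7: the same steps give 80%.
- AR(1) 0.7: window variance (3 + 4 × 0.7 + 2 × 0.49)/9 = 0.753; correlation between windows 0.495; variance of the difference 2 × 0.753 × (1 − 0.495) = 0.761. The fall is 2.80 × √0.753/2 = 1.22, and 1.22/√0.761 = 1.39. Power = Φ(1.39 − 1.96), about 29%.
- AR(1) 0.9: 61%.

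**Months 1-3 under the SAP.** The mean of three 30-night proportions is the 90-night count divided by 90. The SAP's t-test is therefore already one averaged comparison for that window.

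**The case against.** The strongest reply is that the hypotheses refer to the difference over a span of months in the singular, which fits one averaged contrast. The sentence about testing each month could be a separate statement about model output. A reader might infer that each hypothesis must carry either an inflated error rate or less than 80% power. The documents do not support that: the averaged reading avoids both, and Bonferroni over the months holds alpha and keeps power above 80% for correlations up to about 0.7. What stands is that the protocol does not choose among these readings.

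Second, the later SAP removes the difficulty for months 1-3, and the main Aim 1 analysis is unaffected. That is correct. The SAP text is headed as covering primary outcomes, so its silence on 1b and 1c may mean they are secondary rather than dropped. Either way, their only rule is the protocol's.

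Third, the protocol regards differences under 10 points as not clinically meaningful, and at 10 points the every-month rule loses little. That also stands, but only on the SD of 0.0913. That SD has no between-person component, while correlated months imply one. The any-month error rate does not depend on effect size.

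Fourth, a reader might infer that a sustained effect will be declared because both windows are separately significant. No section says so. The protocol promises a statistical separation of the patterns and leaves the method unnamed.

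**Conclusion.** The point holds for 1b and 1c: the decision rule is undefined, no multiplicity adjustment is given, and the power figure covers one month only. Of the natural readings, any-month raises the type I error to about 8-11% (3 months) or 11-23% (7 months). Every-month lowers power to 64-72% or 44-67% at the 7-point effect. One averaged contrast does neither. These ranges rest on an assumed correlation of 0.7 to 0.9 and a constant effect within the window; the 7-month figures also assume full data.

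This does not threaten the SAP's 90-night comparison. Nor do the documents show that any hypothesis will in fact be declared from a single month. The plan leaves that choice open, and it is cheap to close before the data are analysed.

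**What to change.** State in the SAP whether 1b and 1c are retained. For each one retained, pre-specify a single 1-df contrast from the mixed model: the BEST-minus-control difference averaged with equal weight over the months of the window. Make the monthly differences descriptive, and restate the power for the window contrasts, allowing for reduced numbers after month 6 in 1c.

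For maintenance versus diminution, report the arm difference in months 4-6 minus that in months 1-3, with a 95% CI, as an estimate. Do not read a non-significant result as a sustained effect, since power to detect a halving runs from about 29% to over 99% depending on the correlation structure.

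The cost is a few sentences and a contrast statement, with no change to data collection or sample size. The downside is that month-specific p-values are no longer confirmatory.

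### Month 6 is assigned to both Hypothesis 1b and Hypothesis 1c, and the N=56 power stated for Hypotheses 1a-c is supported only for months 1-6

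*Protocol*

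**What the plan says.** All of the following is in Protocol Section 4.6b unless stated otherwise.

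- **Time scale.** Adherence is computed for the first 30 days and then "for each subsequent 30-day period (months 2-12"). In the mixed model, time is a categorical factor with 12 levels, and the group difference is tested at each month.
- **Windows.** H1a concerns months 1-3. H1b "will be assessed by testing the significance of the difference in adherence rates between the BEST program and control groups in months 4-6". H1c tests "the significance of the difference in the adherence rates between the BEST program and control groups in months 6-12".
- **Available data.** "All participants will be measured for at least 180 days, thus providing at least 6 months of data for all participants". After that, "PAP adherence rates beyond month 6 will be computed for participants who enrolled early enough to provide such data". The mixed-model paragraph repeats that "only some participants will have data beyond six months".
- **Power.** The paragraph headed as covering Hypotheses 1a-c says that "the power with respect to Aim 1 was computed assuming a sample size of N=56 with complete data". It gives an SD of 0.0913, a detectable difference of 7% for a given month at 80% power, power of .98 for a 10% difference, and power above .999 for 20%. It treats differences below 10% as not clinically meaningful.
- **Origin of N=56.** Section 4.6a and the sample size overview derive it from Aim 2: 62 randomized, less a 10% allowance for missing data at the 3-month follow-up, leaving 28 per group.
- **SAP.** The later SAP (April 2020; the protocol is dated April 2019) has a single Hypothesis 1 for Aim 1: a two-sample t-test on nights of use out of 90. It mentions neither H1b nor H1c.

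**The concern.** There are two faults in how H1c is specified.

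First, month 6 is one discrete level of the time factor, and it is assigned to two hypotheses. H1a and H1b meet without overlapping (1-3, then 4-6), so the H1c window is the one out of line. The protocol's own dividing line is the end of month 6, because follow-up is promised to everyone up to that point and not after it. As written, H1c combines a month in which everyone is followed with months in which only earlier enrollees are.

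Second, the power statement names H1c but uses a sample size that the protocol does not promise for months 7-12. H1c is the long-term maintenance question. If its precision is overstated, a non-significant result late in follow-up could be taken as evidence that the effect had faded, when it may only reflect a smaller sample.

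**Working it through.** **1. The windows.** H1b uses months {4, 5, 6} and H1c uses months {6, 7, 8, 9, 10, 11, 12}. The intersection is {6}, which is days 151-180. The promised follow-up of 180 days is 6 × 30, so it ends exactly with month 6. Month 6 is therefore the only H1c month in which all participants are due to be followed.

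**2. Reproducing the stated power.**

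Inputs:
- SD = sqrt(0.5 × 0.5 / 30) = 0.0913 (Section 4.6b).
- n = 28 per group (Section 4.6a).
- alpha = 0.05 (Section 4.6b). Two-sided testing is stated for Aim 2 in Section 4.6c and is assumed here for Aim 1.

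Method: power from the noncentral t distribution with 2n − 2 degrees of freedom and noncentrality = difference / (SD × sqrt(2/n)). The detectable difference is d × SD, where d is the standardized difference that gives 80% power.

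At n = 28:
- Detectable difference: d = 0.762, and 0.762 × 0.0913 = 0.0696, or 7.0 points.
- Power at 10 points: standard error = 0.0913 × sqrt(2/28) = 0.0244; noncentrality = 0.10 / 0.0244 = 4.10; power = 0.98.
- Power at 20 points: above 0.999.

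All three stated figures reproduce with the full 28 per group.

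**3. The same calculation for a single month after month 6.** The documents give no count for these months. The share of the 56 with data is therefore an assumption, shown as a range. SD and alpha are unchanged.

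| Assumed share of 56 | n per group | d for 80% power | Detectable difference (d × 0.0913) | Power at 7 points | Power at 10 points | Power at 20 points |
|---|---|---|---|---|---|---|
| 100% | 28 | 0.762 | 7.0 points | 0.80 | 0.98 | >0.999 |
| 75% | 21 | 0.886 | 8.1 points | 0.68 | 0.93 | >0.999 |
| 50% | 14 | 1.100 | 10.0 points | 0.50 | 0.80 | >0.999 |
| 25% | 7 | 1.632 | 14.9 points | 0.26 | 0.47 | 0.96 |

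The 10-point column matters most, because 10 points is the protocol's own threshold for clinical relevance.

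**4. Is a shortfall plausible?** Section 4.3 starts recruitment in Detroit, adds Ann Arbor 3 months later, and adds Cleveland 3 months after that. The Table 1 footnote gives Cleveland 300 of the 591 people in the recruitment sample (300/591 = 51%). The largest source thus opens six months after the first. This makes later entry likely for many participants, but it does not give a number with data in months 7-12. The shading of the project timeline in Section 6.1 is not legible in the text available, so the planned extent of additional monitoring cannot be read from it.

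**The case against.** **The stated power is for a given month.** This is correct, and it makes N=56 fair for any of months 1-6, including month 6. It does not extend to months 7-12, which the paragraph's heading includes.

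**The overlap has no demonstrated numerical effect.** This stands. The group difference is tested at each month, and the protocol does not say that the months in a window are pooled. A reader might infer that month 6 is counted twice in a pooled estimate, or that H1b and H1c are distorted by shared data. The documents do not support that. The overlap looks like a labelling slip to be corrected.

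**N=56 may still hold.** A reader might also infer that 56 participants cannot exist in months 7-12. That goes too far. The protocol says only that some participants will have such data; if 56 of the 62 did reach month 12, the stated power would stand. The point is that the documents do not support the figure, not that they refute it.

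**The mixed model accommodates incomplete data.** It does, and it may borrow some strength across months. It does not restore the between-group information of 28 per group in months when fewer are observed. The expectation in Section 4.6a of no further attrition after 3 months concerns dropout, not the shorter follow-up of late enrollees.

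**A multi-month average would be more precise.** Under the same binomial model, an average over months 7-12 uses 180 nights, so SD = sqrt(0.25/180) = 0.0373, and 7 per group could detect 1.632 × 0.0373 = 0.061, or 6.1 points. This stands as arithmetic, and it is why the table applies to single months only. Both SDs, however, contain only night-to-night binomial variation and leave out variation between people. That is a separate and probably larger matter that affects H1a, H1b and H1c alike: with an assumed between-person SD of 0.30, power at 10 points is about 0.23 even at 28 per group.

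**The SAP omits H1c, and the protocol already plans to examine maintenance against diminution.** Both are true, and they reduce the practical weight. The SAP does not say that H1b and H1c were withdrawn, however, so their status is open.

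**Conclusion.** The point holds, at minor to moderate weight. Month 6 is assigned to two hypotheses, and the power stated for Hypotheses 1a-c rests on a sample size that the documents support only for months 1-6.

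For a single month after month 6, at the protocol's SD, the detectable difference is 8.1, 10.0 or 14.9 points rather than 7.0, and power at 10 points is 0.93, 0.80 or 0.47 rather than 0.98, if 75%, 50% or 25% of the 56 have data. The shares are assumptions, and two-sided testing is assumed for Aim 1. At half the sample, the protocol's relevance threshold still has about 80% power, and a 20-point difference keeps at least 0.96 throughout the range. The loss is serious only towards the low end.

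A reader might conclude that the trial's main adherence result or its sample size is undermined. The documents do not support this: N=62 is set by Aim 2, and the SAP's Aim 1 test uses the first 90 nights only.

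**What to change.** 1. Define H1c as months 7-12, so that the three windows do not overlap.
2. Limit the stated power paragraph to H1a and H1b.
3. Label H1c exploratory, and give it its own detectable difference at the number expected to have data in months 7-12 under the staggered enrolment schedule. Say whether that figure is for one month or for an average over the window. Who contributes is already governed by enrolment date in Section 4.6b, and that rule can stay.
4. Reconcile the protocol with the SAP by stating whether H1b and H1c are retained. If they are, the SAP needs their analysis; if not, it should say that they were dropped.

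The cost is a few lines of wording, one recalculation, and a less favourable power figure for H1c if fewer than 56 are expected. No change to the sample size or data collection follows.
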